A Pilot Study of Subclinical Leaflet Thrombosis in Bioprosthetic Aortic Valves: A Randomized Controlled Trial

Principal Investigator: [name]

Introduction

A recent study published in the *New England Journal of Medicine* identified reduced aortic-valve leaflet motion in patients with bioprosthetic aortic valves. Based upon the observation that this finding resolved with therapeutic anticoagulation, the authors suggested that reduced leaflet motion may be attributable to subclinical leaflet thrombosis. The incidence of reduced leaflet motion varied from 7.4% after surgical aortic valve replacement (SAVR) to 43% after transcatheter aortic valve replacement (TAVR). Altered leaflet motion was detected with both 4-dimensional contrast-enhanced cardiac multidetector computed tomography(MDCT) and transesophageal echocardiography (TEE), but could not be identified on transthoracic echocardiography (TTE). The clinical significance of this finding is uncertain.

The true incidence of this finding and the impact of periprocedural anticoagulation on leaflet motion are unknown. In addition, our review of available MDCT scans from the NEJM article raises questions concerning the validity of reduced leaflet motion after SAVR. Therefore, we propose a prospective, randomized pilot study in patients undergoing SAVR and TAVR to 1) Estimate the incidence of reduced leaflet motion and 2) Assess the impact of perioperative anticoagulation on the incidence of reduced leaflet motion. Data from this pilot study will enable us to determine the feasibility of a larger randomized controlled clinical trial to investigate the phenomenon of reduced leaflet motion/subclinical valve thrombosis and, possibly, its clinical importance.

Background and Significance

Aortic valve replacement prolongs survival in patients with severe aortic valve disease. Over the last decade, there has been a gradual shift to bioprosthetic valves in the surgical arena. TAVR involves implantation of bioprostheses, making bioprosthetic aortic valve replacement the most common overall treatment for severe aortic valve disease.

The need for periprocedural warfarin after bioprosthetic aortic valve replacement is uncertain. While some centers treat patients with warfarin for 6 to 12 weeks after bioprosthetic SAVR, others (including the Cleveland Clinic), employ a strategy of aspirin alone. A recent Scandinavian registry-based study suggests that short-term warfarin may improve outcomes after SAVR, but there are no large, prospective studies that validate this strategy.

Anticoagulants are also used to treat TAVR postoperatively. Typically patients will be on aspirin and clopidogrel for 12 weeks before switching them to aspirin alone. Patients who are on warfarin for atrial fibrillation may be treated with warfarin and clopidogrel for 3 months, while others are treated with aspirin and warfarin. No substantial research has shown one treatment to be more effective than the other.

The observation of reduced leaflet motion after SAVR and TAVR with the possibility of subclinical valve leaflet thrombosis has reignited the debate over periprocedural anticoagulation. The authors of the recent NEJM study point out that we need "better characterization of this observation ...to determine its frequency and evaluate its clinical effect." The purpose of this pilot trial is to determine the frequency of reduced leaflet motion after SAVR and TAVR and to determine whether perioperative anticoagulation with warfarin impacts this frequency.

Study Design

Methods: This will be a pilot prospective randomized controlled trial.

Sample: The study will enroll 50 adult patients scheduled to undergo SAVR and 50 adult patients scheduled to undergo TAVR.

Inclusion Criteria

Scheduled for SAVR or TAVR with or without the following concomitant procedures:

- Tricuspid valve surgery
- PFO closure
- ASD closure
- MV repair
- Myectomy

Age \geq 18 years

Able and willing to give informed consent

Able and willing to return for follow up

Exclusion Criteria

Contraindications to warfarin, Plavix or aspirin

Pre-existing medical indication for warfarin, Plavix or aspirin

History of previous coronary artery stenting

Requirement for concomitant coronary artery bypass grafting or mitral valve replacement

Contraindications to contrast-enhanced MDCT including anaphylactic iodine allergy, History of atrial fibrillation

Renal dysfunction (GFR < 60 ml/min).

Research Procedures

Screening

Patients scheduled for SAVR or TAVR will be identified by nurse practice managers and their records examined to determine eligibility. Potential subjects will be contacted by a research nurse, who will determine the presence of Inclusion/Exclusion Criteria. Subjects who satisfy Inclusion/Exclusion Criteria will be approached for informed consent. Those who give informed consent will be enrolled.

Review of medical records will be done to obtain medical history.

Intra-op Aortic Valve Procedure

Randomization and Anticoagulation/Antiplatelet Regimen

After induction of anesthesia, a computer program will be used to randomize patients to one of the treatment groups below, according to their scheduled procedure:

SAVR

Warfarin group (n=25)

Warfarin treatment for 12 weeks with a target INR of 2-3 Warfarin treatment to begin on postoperative day 1-3 according to the patient's clinical status

When warfarin treatment is discontinued, patients will be treated according to standard of care (aspirin 81 mg/day) indefinitely

Aspirin group (n=25)

Aspirin (81 mg/day) to begin within 1-3 postoperative days according to the patient's clinical status and continue indefinitely per standard of care.

TAVR

Warfarin group (n=25)

Begin Warfarin and Aspirin (81 mg/day) treatment within 1-3 days postop for 12 weeks with a target INR of 2-3

At 12 weeks, study treatment will end and patients will be treated according to standard of care (aspirin 81 mg/day) indefinitely

Aspirin group (n=25)

Begin aspirin (81 mg/day) and clopidogrel (75 mg/day) in periprocedural period and continue for 12 weeks
At 12 weeks, study treatment will end and patients will be treated according to standard of care (aspirin 81 mg/day) indefinitely

A transesophageal echo (TEE) will be performed prior to implant Patients will undergo SAVR or TAVR according to standard clinical protocol.

Follow up

Patients will be seen at 4-6 weeks postoperatively for the following procedures:

- TTE
- 4D MDCT scan
- Review of medical history

At 6 months (+/- 7days), 9 months (+/- 7days) and 12 months (+/- 7days) post operatively, patients will be contacted by phone to assess for change in medications, assessment of bleeding, stroke, TIA or MI signs and symptoms, and to obtain any INR results and imaging tests if done.

Imaging

Baseline intraoperative TEE

Periprocedural TEE will be performed to confirm normal bioprosthetic aortic valve function and establish a "valve footprint". This will include standard2D, spectral Doppler, color Doppler, full volume 3D and live 3D acquisitions. In addition, baseline aortic valve gradients will be recorded.

Transthoracic echocardiography (4-6 weeks post-procedure)

All patients will undergo a clinically indicated comprehensive TTE. Along with standard chamber dimension assessment, we will record LV outflow tract diameter in a standard fashion on parasternal long-axis view. Pulsed-wave and continuous-wave Doppler will be used to record velocities across the LV outflow tract (LVOT) and AV, respectively. AV will be examined from multiple windows including apical, suprasternal and right parasternal to obtain the peak AV velocity and the mean AV gradient. Additionally, dimensionless index will be calculated using the ratio of velocity time integral of LVOT obtained on pulse wave velocity divided by velocity time integral across aortic valve on continuous wave Doppler. AVA will be calculated using the continuity equation. In addition, attempts will be made to visualize AV leaflets and assess mobility as described below in "leaflet motion analysis".

Contrast enhanced 4D MDCT

All subjects will be scanned on standard MDCT scanners (Definition Dual Source/Definition Flash, Siemens Medical Solutions, Erlangen, Germany; or Brilliance 256-slice, Philips Medical Systems, Best, The Netherlands) after administration of iodinated contrast (80-100 mL of Ultravist 370) at 4-5 mL/s followed by 30-50 mL of normal saline. Bolus tracking technique using a region of interest in ascending aorta will be used, and scanning (from the carina to the mid left ventricle) will be performed initiated in the craniocaudal direction during a single inspiratory breath-hold. Spiral data will be acquired with retrospective electrocardiogram gating using the following parameters: gantry rotation time=270-330 ms; beam collimation ranging from 128 x 0.6 mm to 32 x 0.6mm; tube voltage=100-120 kVp; tube current adjusted per patient weight; and beam pitch of 0.2-0.5. Electrocardiogram-based tube current modulation will be used for all patients, with maximum current turned on between 30-70 % phases of the cardiac cycle (hence maintaining image quality during the systolic phases). 4dimensional images will be reconstructed during 10 phases of the cardiac cycle with a section thickness of 0.75 mm. Radiation in the study sample will typically be < 12 mSEV.

Leaflet motion analysis

Based upon the 4D MDCT data, we will attempt to measure leaflet tip thickness. In addition, leaflet motion will be judged as normal, mildly reduced (<50% reduction in motion), moderately reduced (50 to 70% reduction), severely reduced (>70% reduction), or immobile (lack of motion of at least one valve leaflet). For the purposes of analysis, leaflet motion will be considered reduced if it is moderately reduced, severely reduced, or immobile. The 4D CT scans will be interpreted by a reviewer who is blinded to the anticoagulation/antiplatelet regimen for the patient.

Crossovers

Patients who are randomized to an aspirin group and who develop a new indication for periprocedural anticoagulation (e.g. perioperative atrial fibrillation) will be crossed over into the warfarin group. Patients who are randomized to a warfarin group who develop contraindications to warfarin will be crossed over to the aspirin group. Patients who are randomized to an aspirin group who develop overt leaflet thrombosis, as detected by clinical standard of care imaging may be treated with warfarin at the discretion of the treating physician. However, the physicians will be blinded to the results of the 4D MDCT scan till the completion of the study.

Funding

Funding will be provided by the [name] treasury fund (000000991924, T56338).

Adverse Events and Independent Medical Safety Officer

Adverse events will be reported directly to the IRB.

An Unanticipated Problem Involving Risks to Participants or **Others** is any event that (1) is unforeseen, (2) caused harm or placed a person at increased risk of harm, and (3) is related to the research procedures.

An Adverse Event (AE) defined for this pilot study is any untoward or unfavorable medical occurrence related to structural valve deterioration, bleeding, stroke, TIA or MI.

A Serious Adverse Event (SAE) is any adverse experience that results in any of the following outcomes:

- 2 death
- a life-threatening experience
- ☐ inpatient hospitalization or prolongation of existing hospitalization
- a persistent or significant disability/incapacity
- ② a congenital anomaly/birth defect
- Important medical events that may not result in death, be life-threatening, or

require hospitalization may be considered a serious adverse drug experience when, based upon appropriate medical judgment, they may jeopardize the patient or subject and may require medical or surgical intervention to prevent one of the outcomes listed in this definition.

The independent Medical Safety Officer will routinely review all deaths, SAEs, adverse events and imaging. The medical safety officer will be separate and independent from clinical staff or anyone responsible for patient care.

Statistical Analysis

A statician will analyze using the following: Standard descriptive analysis will be performed. Continuous variables will be compared using t-testing or analysis of variance. Categorical variables will be compared using Chi-square. Outcomes will be compared in 2 groups using standard survival analysis. Predictors of 30-day outcomes will be determined using logistic regression analysis. All analysis will be done by standard software (SPSS and SAS). A p-value <0.05 will be considered significant.

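### In SAVR, randomising at induction when both arms start drug 1-3 days later builds in avoidable pre-dose crossovers that dilute the estimated effect

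*Combined protocol and SAP*

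**What the plan says.** Under Randomization and Anticoagulation/Antiplatelet Regimen, allocation comes at the start of the operation: "After induction of anesthesia, a computer program will be used to randomize patients to one of the treatment groups below". The same section then gives the baseline echo ("A transesophageal echo (TEE) will be performed prior to implant") and the valve procedure.

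First doses come later:

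- SAVR warfarin: "Warfarin treatment to begin on postoperative day 1-3"
- SAVR aspirin: "Aspirin (81 mg/day) to begin within 1-3 postoperative days"
- TAVR warfarin: "Begin Warfarin and Aspirin (81 mg/day) treatment within 1-3 days postop"
- TAVR aspirin plus clopidogrel: "Begin aspirin (81 mg/day) and clopidogrel (75 mg/day) in periprocedural period"

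The Crossovers section states that aspirin-arm patients "who develop a new indication for periprocedural anticoagulation (e.g. perioperative atrial fibrillation) will be crossed over into the warfarin group". It requires the reverse switch for warfarin-arm patients in whom warfarin becomes contraindicated.

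Exclusion Criteria already rule out a history of atrial fibrillation, existing indications or contraindications for the study drugs, and "Requirement for concomitant coronary artery bypass grafting or mitral valve replacement". Under Screening, eligibility is determined before consent. No re-check between surgery and first dose is described. Statistical Analysis names no analysis set.

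**The concern.** Nothing in the SAVR operation as described depends on the allocation, and neither SAVR arm acts on it until postoperative day 1 at the earliest. The protocol's own example of a crossover trigger, perioperative atrial fibrillation, can fall in that interval. The result is inconsistent. Atrial fibrillation known at screening excludes a patient, while atrial fibrillation on the day after surgery keeps an aspirin-arm patient in the trial and moves that patient to the other regimen. An unplanned bypass graft raises a similar problem, because the patient is already in an arm when the exclusion comes to apply.

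A pre-dose switch is the most diluting kind. The patient reaches the 4-6 week CT without ever having taken the allocated regimen, whereas a later switch follows partial exposure. One of the two stated aims is to assess the impact of anticoagulation on reduced leaflet motion, and the results are meant to show whether a larger trial is feasible. An estimate pulled towards zero by avoidable crossover is a poor basis for that.

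**Working it through.** **Sequence in SAVR.** Screening and consent; induction; randomisation; TEE; implant; first dose on day 1-3. The crossover triggers can act between randomisation and first dose. The plan states no crossover rate, power or effect size, so there is no figure of its own to reproduce.

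**Dilution.** Let pA and pW be the incidences of reduced leaflet motion under aspirin and warfarin, c the fraction of the aspirin arm switched before dosing, and d the fraction of the warfarin arm switched before dosing. Assume that switched patients have the same underlying risk as the others.

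- Aspirin arm as randomised: pA(1-c) + pW·c
- Warfarin arm as randomised: pW(1-d) + pA·d
- Difference: (pA - pW)(1-c-d)

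**Illustration for SAVR.** Inputs: pA = 7.4% (Introduction, cited as background) and 25 per arm (protocol). Assumed: d = 0, warfarin halves the incidence (pW = 3.7%), two-sided 0.05. The last column is the size a larger trial would need to detect the diluted difference (normal approximation).

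| c (assumed) | Expected switches of 25 | Factor 1-c | Difference, points | n per arm for 80% power |
|---|---|---|---|---|
| 0 | 0 | 1.0 | 3.70 | 600 |
| 10% | 2.5 | 0.9 | 3.33 | 718 |
| 20% | 5.0 | 0.8 | 2.96 | 879 |
| 30% | 7.5 | 0.7 | 2.59 | 1110 |

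The last column rises 1.20, 1.47 and 1.85 times, close to the rule of thumb 1/(1-c)², which gives 1.23, 1.56 and 2.04. Switches in the other direction add to the loss: c = 20% with d = 5% leaves 0.75 of the difference.

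**Power in the pilot itself.** Take the most favourable case, pW = 0. With 0 events on warfarin, the uncorrected chi-square at 25 v 25 needs at least 4 events on aspirin:

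- 4 v 0: pooled rate 4/50 = 0.08; 0.16² / (0.08 × 0.92 × 2/25) = 4.35, above 3.84
- 3 v 0: 3.19, below 3.84

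Power is therefore the probability of 4 or more events among 25 at 7.4%, which is 10.9%. With c = 10%, 20% and 30% it is 8.1%, 5.7% and 3.8%. If warfarin halves the incidence, it is 4.8% without crossover and 3.1% at c = 30%. SAVR cannot show a difference whichever timing is used, so the case for moving randomisation rests on estimation.

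**TAVR.** The warfarin arm starts 1-3 days after the procedure; the comparator starts in a periprocedural period that is not defined. Randomising straight after implant would screen out intraoperative events only. Atrial fibrillation or a contraindication in the following days would still come after allocation, and the warfarin arm's gap before first dose would largely remain.

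**The case against.** The strongest reply is that this is a reasonable trade-off in a pilot. Crossover frequency is itself a feasibility result, screening out patients with early events narrows the population, and the crossover rate and its pre-dose share are unknown. Much of this stands. Switches after the first dose would continue under any timing, so only the pre-dose share is recoverable. The feasibility information need not be lost, however, if patients not randomised are counted with reasons.

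Three stronger readings are tempting, and the documents do not support them.

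- **A large TAVR power loss caused by timing.** With 43% incidence on control and an assumed 10% on warfarin, exact chi-square power at 25 per arm falls from 80% to 73%, 64% and 54% as aspirin-arm crossover rises to 10%, 20% and 30%. The arithmetic is right, but it describes total crossover at assumed rates, in the arm whose gap before first dose is undefined and may be short. Randomising after implant would not recover most of it.
- **Allocation influencing the operation.** The protocol does not say who receives the allocation, and the CT reader is blinded to regimen. Influence on the procedure or the baseline TEE is possible but not shown. Withholding the allocation from the operating team would deal with it without moving randomisation.
- **Broken randomisation.** Counting patients in the arm they crossed into would do this, but it is a matter of the unstated analysis set, which later randomisation does not settle.

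**Conclusion.** The point holds for SAVR. Followed as written, the plan allocates patients before a 1-3 day interval in which its own mandatory crossover triggers can occur, with no need for the allocation until that interval ends. The as-randomised difference is multiplied by (1-c-d). For c between 10% and 30% and d = 0, it keeps 90% to 70% of its size. Those rates are assumptions, as is equal underlying risk in patients who switch.

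The harm is a diluted estimate, and a larger trial planned from it, rather than lost power in the pilot: SAVR power is about 11% or less at 7.4% incidence either way. For TAVR no gain in power should be claimed. This is a worthwhile, inexpensive improvement and not a defect that invalidates the trial.

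**What to change.** - Keep consent before surgery. In SAVR, run the same computer randomisation immediately before the first study dose, within the existing day 1-3 window.
- Re-confirm the existing eligibility criteria at that moment, including no new indication, no new contraindication and no unplanned bypass graft. Do not randomise patients who no longer qualify; replace them so that 25 per arm are randomised.
- Log the number not randomised and the reasons as a feasibility result. Where such patients are scanned, report their leaflet-motion incidence separately.
- Leave the regimens unchanged.
- In TAVR, the sponsor should first reconcile the start times stated for the two arms, and then decide where randomisation fits.

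As a side benefit, allocation after implant cannot affect the operation or the baseline TEE.

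The cost is a protocol wording change, running the program on the ward, and enrolling replacements for consented patients who are never randomised. The randomised comparison would then apply to patients without an early new indication or contraindication, and the report should say so.

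### Structural valve deterioration is a defined adverse event but is not queried at the 6, 9 and 12 month calls, so late valve events could be under-ascertained

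*Combined protocol and SAP*

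**What the plan says.** In the combined protocol and SAP, the section on adverse events and the Medical Safety Officer defines an adverse event for this pilot as "any untoward or unfavorable medical occurrence related to structural valve deterioration, bleeding, stroke, TIA or MI". Hospitalisation is among the criteria that make an event serious. The Medical Safety Officer reviews deaths, serious and other adverse events, and imaging.

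Under Follow up there is one visit: "Patients will be seen at 4-6 weeks postoperatively for the following procedures", namely TTE, 4D MDCT and a medical history review. The later contacts, at 6, 9 and 12 months, are calls: "patients will be contacted by phone to assess for change in medications, assessment of bleeding, stroke, TIA or MI signs and symptoms". The same sentence gives the calls one further purpose, which is to collect outside results: "and to obtain any INR results and imaging tests if done".

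Under Crossovers, "the physicians will be blinded to the results of the 4D MDCT scan till the completion of the study". The Statistical Analysis section compares outcomes by survival analysis without naming those outcomes.

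**The concern.** The definition of an adverse event and the content of the calls do not match. The calls repeat four of the five conditions and leave out the first. They also do not ask about symptoms of valve dysfunction, hospital admission or valve re-intervention. A valve event after the 4-6 week visit therefore depends on passive capture, while the other four conditions are asked about directly.

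Three features of this trial make that gap worth closing:

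- Treating physicians do not see the 4D MDCT result, so a CT finding of reduced leaflet motion will not itself prompt them to look at the valve again.
- Study treatment lasts 12 weeks and the first call is at 6 months, so no scheduled contact falls soon after treatment stops.
- The only stated blinding to regimen is that of the CT reader. Clinicians who know the regimen could order imaging at different rates in the two arms.

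At stake are the completeness of the safety data and the comparability of any valve-event analysis between arms.

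**Working it through.** The plan gives no figure to reproduce here, so the check is mainly a comparison of sections.

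**Step 1. Adverse event definition against call content.**

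| Condition in the definition | Signs and symptoms queried at 6, 9 and 12 months? |
|---|---|
| Structural valve deterioration | No |
| Bleeding | Yes |
| Stroke | Yes |
| TIA | Yes |
| MI | Yes |

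One of five is missing, and it is the only one missing.

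**Step 2. Other planned routes to a late valve event.**

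- Scheduled imaging: the TTE and the 4D MDCT are each planned once after the procedure, at 4-6 weeks. None is scheduled later.
- Imaging done in ordinary care: collected at the calls if it was done. This is the one direct route.
- Medication changes: asked at the calls. This could reveal warfarin started for overt leaflet thrombosis, but only indirectly.
- Criteria: none are given for structural valve deterioration, so a retrieved report has no stated standard to be judged against.

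**Step 3. Time covered.** From week 6 to week 52 is 52 - 6 = 46 weeks, or 46/52 = 88% of the year. Taking 6 months as about 26 weeks, the interval from the end of study treatment to the first call is 26 - 12 = 14 weeks. These figures give the length of the period; they do not give the share of events missed.

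**Step 4. Can the under-count be sized?** Not from the documents. As an illustration under assumption only: suppose late deterioration is found only by imaging, and a share f of affected patients are imaged clinically and reported. The share missed is 1 - f.

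| Assumed f | Share missed |
|---|---|
| 0.25 | 75% |
| 0.50 | 50% |
| 0.75 | 25% |

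If the true rate p is the same in both arms but f differs, the observed ratio is (p × f1)/(p × f2) = f1/f2. With f1 = 0.75 and f2 = 0.50 this is 0.75/0.50 = 1.5, an apparent difference where none exists. Neither p nor f is given, so this shows the mechanism, not its size.

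**The case against.** The strongest reply is that the calls are broader than a list of four events. They ask about medication changes and collect imaging, which is the natural evidence for valve deterioration, on all three occasions. A patient with symptomatic valve dysfunction or a re-intervention may well have been imaged, and the Crossovers section expects standard-of-care imaging to detect overt leaflet thrombosis. The 4-6 week TTE is not withheld from clinicians and records gradients and valve area. This stands: capture is incomplete and passive, not absent.

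It is also fair that the pilot's two aims, the incidence of reduced leaflet motion and the effect of anticoagulation on it, rest on the 4-6 week CT. The Introduction leaves clinical importance to a larger trial, and only as a possibility. That stands too.

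Several stronger readings are tempting, and the documents do not support them:

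- A reader might infer that valve events would be close to nil whatever the truth. Without a rate of deterioration or of clinical imaging, this cannot be shown.
- A reader might infer that the Medical Safety Officer would be kept from the relevant signal. The masking sentence covers the physicians; the officer reviews imaging and is not stated to be masked to the CT.
- A reader might apply the Introduction's rates (50 × 0.074 = 3.7 and 50 × 0.43 = 21.5, together 25.2) and take about 25 of 100 patients as the number at stake. That would estimate abnormal CTs, not missed valve deterioration. It also ignores that half the patients are assigned warfarin, and the Introduction itself calls the true incidence unknown.

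What the reply does not answer is the mismatch itself: one defined adverse event is left to whether someone else ordered a test.

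**Conclusion.** The point holds in a limited form. Structural valve deterioration is the only one of the five defined conditions that the late calls do not query, and no study imaging is scheduled after 4-6 weeks. Late valve events could be under-ascertained, and unevenly by arm if clinical imaging is ordered more often in one arm. The size is unknown, and differential imaging is a possibility rather than something the documents show.

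The consequence is confined to safety ascertainment and to any survival analysis whose outcomes include valve events. The plan does not say whether they do. The main aims are unaffected. The change is worth making because it is cheap and brings the follow-up into line with the plan's own definition.

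**What to change.** Add a short valve block to the three calls already scheduled: valve-related symptoms, any hospital admission, any valve re-intervention, and death (from a proxy or the record). For a positive answer, retrieve the clinical records and any echo already done, and compare the echo with the patient's own 4-6 week TTE. State in advance the criteria for structural valve deterioration. Send each case to the Medical Safety Officer. Tabulate these events by randomised arm within SAVR and within TAVR, and state whether they enter the survival analysis.

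If the sponsor prefers not to change the calls, the plan should at least say that valve deterioration after the 4-6 week visit is not systematically ascertained, so that a low count is not read as evidence of safety.

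The change needs no added scan, visit or change of treatment. The cost is slightly longer calls, record retrieval for positive answers, and review of some symptoms that prove unrelated to the valve.

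### The crossover rule moves patients between groups named as the randomised arms, and the analysis plan never says that the groups compared are as randomised

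*Combined protocol and SAP*

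**What the plan says.** Randomization and Anticoagulation/Antiplatelet Regimen assigns patients after induction of anaesthesia: "a computer program will be used to randomize patients to one of the treatment groups below, according to their scheduled procedure". The arms are called the warfarin group and the aspirin group, with 25 patients in each, separately for SAVR and TAVR.

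Crossovers then gives two mandatory rules. For an aspirin-arm patient with a new indication for anticoagulation: "e.g. perioperative atrial fibrillation) will be crossed over into the warfarin group". In the other direction: "Patients who are randomized to a warfarin group who develop contraindications to warfarin will be crossed over to the aspirin group". A third sentence covers overt leaflet thrombosis in an aspirin-arm patient. It lets the physician treat with warfarin and mentions no change of group.

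Leaflet motion analysis turns the MDCT reading into a yes/no result: "For the purposes of analysis, leaflet motion will be considered reduced if it is moderately reduced, severely reduced, or immobile". Statistical Analysis tests such results with one sentence, "Categorical variables will be compared using Chi-square", and adds "Outcomes will be compared in 2 groups using standard survival analysis". Neither sentence says whether the groups are those randomised or those formed by the drug taken. No section mentions intention-to-treat, as-randomised, as-treated or per-protocol analysis.

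**The concern.** Background and Significance gives, as one of the trial's two purposes, finding out whether warfarin changes how often leaflet motion is reduced. The same data yield two different chi-square tables, depending on whether a crossed-over patient counts in the assigned arm or in the arm moved to. If 5 of 25 aspirin patients cross and none cross back, a 25 v 25 table becomes 20 v 30.

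Only the comparison by randomised arm has an expected difference of 0 under no drug effect, however the triggers relate to risk. New atrial fibrillation and new contraindications to warfarin arise after assignment and may mark patients whose leaflet risk differs from the rest.

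Timing adds to the problem. The scan belongs to the early visit ("Patients will be seen at 4-6 weeks postoperatively for the following procedures"), while study treatment lasts longer ("Warfarin treatment for 12 weeks with a target INR of 2-3" in the SAVR warfarin arm). A crossover can therefore follow the scan, and literal regrouping would then credit the result to a drug the patient had not yet started.

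The Introduction says the data will help decide whether a larger trial is feasible, so a false signal could carry forward.

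**Working it through.** The plan gives no power, effect size or crossover rate, so there is no figure of its own to reproduce. What follows sizes the literal reading.

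**Inputs from the documents.** Rates of reduced motion P = 0.43 (TAVR) and 0.074 (SAVR), from the Introduction; 25 per arm; chi-square; p < 0.05.

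**Assumptions.** No drug effect; two-sided test; share c of the aspirin arm crosses to warfarin and share d of the warfarin arm crosses to aspirin; those crossing have R1 (from aspirin) or R2 (from warfarin) times the risk of those staying in the same arm.

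**Formulas.**
- Aspirin arm: stayers a0 = P/(1 - c + c·R1); crossers a1 = R1·a0.
- Warfarin arm: stayers w0 = P/(1 - d + d·R2); crossers w1 = R2·w0.
- Regrouped warfarin rate W = [(1 - d)·w0 + c·a1]/(1 - d + c).
- Regrouped aspirin rate A = [(1 - c)·a0 + d·w1]/(1 - c + d).
- False difference = W - A.

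**TAVR, c = 0.4, d = 0.2.**
- R1 = R2 = 2: a0 = 0.43/1.4 = 0.307, a1 = 0.614; w0 = 0.43/1.2 = 0.358, w1 = 0.717. W = (0.8×0.358 + 0.4×0.614)/1.2 = 0.444; A = (0.6×0.307 + 0.2×0.717)/0.8 = 0.410. Difference +3.4 points.
- R1 = R2 = 0.5: a0 = 0.43/0.8 = 0.538, a1 = 0.269; w0 = 0.43/0.9 = 0.478, w1 = 0.239. W = 0.408; A = 0.463. Difference -5.5 points.
- R1 = 2, R2 = 0.5: W = (0.8×0.478 + 0.4×0.614)/1.2 = 0.523; A = (0.6×0.307 + 0.2×0.239)/0.8 = 0.290. Difference +23.3 points.
- R1 = 0.5, R2 = 2: W = (0.8×0.358 + 0.4×0.269)/1.2 = 0.328; A = (0.6×0.538 + 0.2×0.717)/0.8 = 0.582. Difference -25.4 points.
- R1 = R2 = 1: every rate is 0.43. Difference 0.

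**False-positive rate, TAVR.** Exact enumeration of the uncorrected Pearson chi-square, with the numbers crossing binomial and tables with an empty margin counted as not significant:

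| Grouping | Difference (points) | False-positive rate |
|---|---|---|
| As randomised | 0 | 6.2% |
| Regrouped, 40%/20%, ratios 2 and 2 | +3.4 | 5.0% |
| Regrouped, 40%/20%, ratios 0.5 and 0.5 | -5.5 | 6.6% |
| Regrouped, 40%/20%, ratios 2 and 0.5 | +23.3 | 37.5% |
| Regrouped, 10%/4%, ratios 2 and 2 | +3.9 | 6.4% |

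**SAVR.** Aspirin-to-warfarin crossover alone, up to 40%, gives +3.0 points (ratio 2) or -2.6 (ratio 0.5). W - A is proportional to P, so the two-way TAVR extremes scale by 0.074/0.43 to about +4.0 and -4.4 points.

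**Price of analysing as randomised.** Assume warfarin halves the TAVR rate to 21.5%, the drug taken has its full effect, and the triggers are unrelated to risk. Aspirin-arm rate = 0.43(1 - c) + 0.215c; warfarin-arm rate = 0.215(1 - d) + 0.43d.
- No crossover: 21.5 points, power 38.6%.
- c = 0.1, d = 0: 40.85% - 21.5% = 19.4 points, power 32.8%.
- c = 0.4, d = 0.2: 34.4% - 25.8% = 8.6 points, power 10.7%.

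**The case against.** The strongest reply is that Crossovers concerns treatment, not analysis. Each group heading in the randomisation section introduces a drug regimen, so moving to a group can naturally mean receiving that regimen. The section lies outside Statistical Analysis, still identifies patients by the arm to which they were randomised, and never says anyone is analysed elsewhere. This stands. A reader might infer that the plan prescribes an as-treated analysis, and the documents do not support that. The omission is certain; an intention to regroup is not. The wording still needs repair: the thrombosis sentence uses treatment language alone, whereas the other two use the names of the arms, and nothing elsewhere settles the question.

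A second reply is that the size is speculative. This also stands. Crossover rates and risk ratios are assumed. The exclusion of patients with a history of atrial fibrillation, an existing warfarin indication or a contraindication may keep crossover low. A reader might take bias in one direction of crossover as the measure of the problem: +17.6 points in TAVR with 40% crossing from aspirin at ratio 2. The rule works both ways, and adding 20% crossing back at the same ratio cuts this to +3.4. With opposite ratios it grows instead, so one-way figures neither represent nor bound the effect.

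A third reply is that this is a small pilot with weak power under either grouping. That limits the consequence but does not remove it, since the plan sets a significance threshold and names the treatment comparison as a purpose.

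**Conclusion.** The point holds as an omission made worse by wording, and should be fixed. The plan does not define its comparison groups, and its crossover rule, followed to the letter, re-forms them by post-randomisation events.

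Neither the size nor the direction of the resulting bias can be known from the documents. Under the assumed two-way crossover in TAVR it runs from a few points, with a false-positive rate near the as-randomised 6.2%, to more than 20 points in either direction when the two triggers carry opposite prognosis. It is 0 if neither trigger is related to leaflet motion, and small in absolute terms in SAVR. These figures show what is possible; they do not predict what will happen.

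**What to change.** 1. In Statistical Analysis, state that patients are analysed in the arm to which they were randomised, within SAVR and within TAVR.
2. In Crossovers, reword the two sentences so that the patient's treatment changes but the analysis group does not.
3. Label any as-treated analysis as secondary.

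The clinical crossover rules stay as they are. The direct cost is a few sentences. The statistical cost is the dilution and loss of power worked out above: slight at low crossover and substantial if many patients cross both ways. A comparison by drug taken would avoid that loss without bias only if the triggers are unrelated to risk, which is why it belongs in a secondary role.
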